4.1.2. Primary Endpoint Failures

- Primary endpoint failures are 1) subjects who are re-stented during follow-up after the per-protocol stenting period and 2) subjects who have not been re-stented at month 24 but have alkaline phosphatase level exceeding 2 times the level at completion of the per-protocol stenting period.
- Subjects who experience early stent removal or complete distal stent migration without subsequent re-stenting will not be considered failures. If re-stenting occurs, but the

cumulative stenting period does not exceed 12 months, the subject remains eligible for primary endpoint assessment.

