Follow-Up Schedule	
 • Baseline: Subject screening, enrollment, LFTs and symptoms. • Study Treatment Procedure: 
 ○ Group A (MS): Stent Placement ○ Group B (PS): Stent Placement: Two or more 8.5 Fr. or 10 Fr. PS whenever possible • 1 Month Follow-up: 
 ○ Group A (MS): LFTs and symptoms ○ Group B (PS): LFTs and symptoms • Stent Exchange Follow-up: 
 ○ Group A (MS): None ○ Group B (PS): Month 4 and Month 8 • Stent Removal: 
 ○ Group A (MS): Removal at Month 12, LFTs and symptoms ○ Group B (PS): Removal of last stents at Month 12, LFTs and symptoms • Post-Stent Removal Follow-Up 
 ○ Group A (MS): Month 24 – LFTs and symptoms ○ Group B (PS): Month 24 – LFTs and symptoms • Additional ERCP visits as needed 
Note: Recurrent strictures will be treated with a metal stent in Group A (MS) and with plastic stents in Group B (PS) – no cross-over. Re-stenting after the per-protocol 12 month stenting period will be considered primary endpoint failures. Follow-up, however, will continue until Month 24 after initial stent placement for all subjects, in order to assess all secondary endpoints in a comparative fashion for the

	MS and PS arms.
Key Inclusion Criteria	
 • Age 18 or older • Willing and able to comply with the study procedures and provide written informed consent to participate in the study • Chronic pancreatitis • Symptomatic bile duct stricture (defined by cholangitis or persistent jaundice for at least one month or cholestasis associated with at least 3 times normal alkaline phosphatase levels) documented at time of enrollment for naïve stricture or at the time of prior plastic stent placement in strictures that had one prior plastic stent inserted.¹² • Common bile duct stricture based on imaging assessment of dilatation of the common and/or intrahepatic bile ducts

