4.1. Primary Endpoint

4.1.1. Primary Endpoint Definition

Stricture resolution at 24 months.

Stricture resolution at 24 months is defined by the following two criteria being met:

- Absence of re-stenting after the per-protocol stenting period through the 24 month visit
- Absence of cholestasis at the 24 month visit, defined as alkaline phosphatase level not exceeding 2 times the level at completion of the per-protocol stenting period

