4.1.3. Re-stenting

- Re-stenting after the per-protocol 12 month stenting period should only be considered if subjects meet initial criteria for stenting:
 - Symptomatic bile duct stricture (defined by cholangitis or persistent jaundice for at least one month or cholestasis associated with at least 3 times normal alkaline phosphatase level) documented at time of enrollment for naïve stricture or at the time of prior plastic stent placement in strictures that had one prior plastic stent inserted.¹²
 - Common bile duct stricture based on imaging assessment of dilatation of the common and/or intrahepatic bile ducts
- To minimize the risk of recurrent obstructive symptoms due to sludge or stones in the post-stent removal period, every attempt should be made to clear the bile duct of sludge and/or stone (i.e., balloon sweep and/or flushing).

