4.2. Secondary Endpoints

1. Occurrence of adverse events related to the stent and/or the stent placement or removal procedures
2. Number of ERCP procedures through 24 months after initial stent placement
3. Ability to deploy the stent(s) in satisfactory position
4. Stent Removal:
 - Ability to remove the stent(s) without serious stent removal related adverse events at each procedure involving removal of stent(s) (technical success at removal) or
 - Complete distal migration without serious stent removal related adverse events
5. Liver Function Tests (LFT's)
 - Baseline LFTs compared to LFTs taken at time of original plastic stent placement for any subject with a prior plastic stent
 - LFT improvement at 1 month post-study treatment compared to baseline LFTs (and/or compared to LFTs taken at time of original plastic stent placement for any subject with a prior plastic stent)
 - LFTs at month 24 compared to LFTs at removal of last stent (applicable for subjects who had not been re-stented at time of month 24 visit)
6. Health Economic Endpoints:
 - Number of outpatient procedures
 - Number of hospitalizations
 - Duration of hospitalizations

- Length of procedures
- Number of devices

5. Design

The study is designed as a post-market, multi-center, prospective, non-blinded, randomized study. At least 164 subjects (82 per arm) will be treated with 1:1 randomization between Group A and Group B and will be followed through 24 months post-initial stent(s) placement:

- Subjects in the MS arm will be treated with a single metal stent, which will be removed 12 months post-placement.
- Subjects in the PS arm will receive 2 plastic stents when possible. Subjects in this arm will undergo plastic stents exchange/bile duct calibration at 4 and 8 month post-initial stent placement. At each stent exchange, the goal should be to provide progressive stent therapy by increasing the number of plastic stents at 4 months and again at 8 months. Final plastic stent removal will occur 12 months post-initial stent placement.

5.1. Inclusion Criteria:

- Age 18 or older
- Willing and able to comply with the study procedures and provide written informed consent to participate in the study
- Chronic pancreatitis

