7.4.8. Additional ERCP

- Liver Function Tests
- Collection of Liver Function Normal Ranges (required for any visit that results in re-stenting)
- Assessment of Biliary Obstructive Symptoms (required for any visit that results in re-stenting)
- Cholangiogram or other Common Bile Duct Imaging (only to be collected in database if standard of care per institution)
- Adverse Event/Device Malfunction Assessment

NOTE: Recurrent strictures must be treated with a metal stent in Group A (MS) and with plastic stents in Group B (PS) – no cross-over.

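### Resolution is scored only on re-stenting and alkaline phosphatase, so recurrence treated without a stent can count as resolved, and the undefined stenting period lets one late re-stent be scored two ways

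*Protocol*

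**What the plan says.** Protocol 4.1.1 states: "Stricture resolution at 24 months is defined by the following two criteria being met". The two criteria are no re-stenting after the per-protocol stenting period through the 24 month visit, and month-24 alkaline phosphatase no more than twice its level at completion of that period. Protocol 4.1.2 gives the mirror image: "Primary endpoint failures are 1) subjects who are re-stented during follow-up after the per-protocol stenting period and 2) subjects who have not been re-stented" but exceed that limit. SAP 7.3 repeats both and adds no further route.

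On the length of the period, the texts differ:

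- Synopsis, Follow-Up Schedule note: "Re-stenting after the per-protocol 12 month stenting period will be considered primary endpoint failures".
- Protocol 4.1.3 uses the same term: "Re-stenting after the per-protocol 12 month stenting period should only be considered if subjects meet initial criteria for stenting".
- Protocol 5 ties removal to the calendar: "Subjects in the MS arm will be treated with a single metal stent, which will be removed 12 months post-placement". Final plastic stent removal is also at 12 months, and Table 1 places stent removal at months 11-12.
- Protocol 4.1.2 and SAP 7.3 instead say that if a patient is re-stented but the "cumulative stenting period does not exceed 12 months, the subject remains eligible for primary endpoint assessment". No calendar limit is attached.

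The Synopsis and Protocol 7.4.8 and 7.5 require recurrent strictures to be treated with the assigned stent type. SAP 4.1 lists the Enrolled, ITT and Per-Protocol cohorts for the primary endpoint and names none as primary.

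**The concern.** The endpoint is meant to show whether the assigned stenting resolved the stricture. A patient whose stricture needed a different biliary intervention afterwards was not resolved by stenting. Yet that patient meets neither failure route if the intervention works, because effective drainage is what keeps alkaline phosphatase within the limit.

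Separately, the same late re-stent can be classed as a failure or left eligible, depending on which sentence is applied. The trial is non-blinded (Protocol 5). If the reading is first chosen at analysis, it is chosen with outcomes known, for the one endpoint that carries the non-inferiority test.

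**Working it through.** **1. Treatment without a stent.** Take a randomised patient with a recurrence after month 12, treated by surgery, percutaneous drainage or endoscopic dilation alone, with month-24 alkaline phosphatase within the limit.

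- Re-stented after the stenting period? No.
- Alkaline phosphatase above twice the reference? No.
- Score under Protocol 4.1.1, 4.1.2 and SAP 7.3: resolved.
- Effect of the rule to re-stent recurrences: the case is a deviation, but that rule governs treatment and not scoring.
- Effect of the Per-Protocol cohort (Protocol 8.4.3, SAP 4.1): the patient is dropped if the deviation is classed as major, but is not counted as a failure.

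**2. Two readings of the stenting period.** Let L be the month the first stent is lost, R the month of re-stenting and X the month of the later removal. Cumulative stent time = L + (X − R).

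Example: L = 3, R = 14, X = 20. Cumulative time = 3 + (20 − 14) = 9 months.

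- Calendar reading: R is after month 12, so the patient is a failure.
- Cumulative reading: 9 ≤ 12, so the patient stays eligible and is judged on alkaline phosphatase. Stent-free time before month 24 is 24 − 20 = 4 months, against 24 − 12 = 12 planned.

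The readings differ only when R > 12 and cumulative time ≤ 12. For a stent still in place at month 24, cumulative time is L + (24 − R). This is ≤ 12 only if R − L ≥ 12. With L = 3 and R = 14 it is 3 + 10 = 13, outside the protection of 4.1.2. With L = 3 and R = 15 it is 3 + 9 = 12, inside it, and the level at completion of stenting does not yet exist.

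**3. Reference value.** Table 1 schedules liver tests at months 11-12 and at any additional ERCP, and at month 4 or 8 if a plastic-arm patient is not re-stented then. Secondary endpoint 5 names its reference ("LFTs at month 24 compared to LFTs at removal of last stent"). The primary endpoint ties its reference to completion of the undefined period, so the right value follows once the period is defined.

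**4. Size.** The plan states no frequency for these cases. Its sample size is not in dispute. With 66% in both arms, margin 20 points and one-sided 5%, the Farrington-Manning formula needs 69 per arm, and exact power is 83.2% at the stated 74. Using the unpooled variance at 46% vs 66% gives (1.645 + 0.842)² × (0.66×0.34 + 0.46×0.54) / 0.20² = 73.1, so 74.

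Test statistic: z = (metal − plastic + 0.20) / SE, with SE from the rates restricted to a −0.20 difference.

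| Metal | Plastic | Difference | SE | z | p |
|---|---|---|---|---|---|
| 48/82 | 54/82 | −0.0732 | 0.0744 | 1.706 | 0.044 |
| 47/82 | 54/82 | −0.0854 | 0.0745 | 1.538 | 0.062 |
| 44/74 | 49/74 | −0.0676 | 0.0780 | 1.697 | 0.045 |
| 43/74 | 49/74 | −0.0811 | 0.0783 | 1.519 | 0.064 |

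One patient is 1/82 = 1.2 points, or 1/74 = 1.4 points. If both true rates are 66%, the trial lands where one added metal success turns a fail into a pass with probability 3.4% (82 per arm) or 4.1% (74 per arm).

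Next, assume that 2 to 6 points of failures are scored as resolved. The exact chance of false non-inferiority at a true 46% vs 66%, with 82 per arm, is 5.7% with no masking and otherwise:

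| Assumed pattern | 2 points | 6 points |
|---|---|---|
| Equal points in both arms | 5.6% | 5.3% |
| Same share of failures in both arms (metal points shown) | 6.8% | 9.5% |
| Metal only | 9.3% | 21.2% |
| Plastic only | 3.2% | 0.8% |

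Plastic-only masking also lowers power at 66% vs 66% from 86% to 79% and 62%.

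**The case against.** The first gap needs a departure from the protocol. Recurrences must be re-stented with the assigned type, patients in whom endoscopic techniques are contraindicated are excluded (Protocol 5.2), and Protocol 1.1 describes these patients as typically poor surgical candidates. Percutaneous drainage is not mentioned in the documents, and drainage that fails may still be caught by alkaline phosphatase. All this makes the case uncommon. It does not say how to score it.

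The calendar reading has good textual support. The cumulative sentence directly follows the one on early removal and migration, so it can be read as covering re-stents inside the first 12 months, and it promises eligibility rather than success. That is a fair reading, but 4.1.2 sets no calendar limit and nothing ranks it against the Synopsis.

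A reader might infer three stronger points, and the documents support none of them:

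- *That the primary ITT analysis is affected.* No cohort is named as primary, and SAP 3.1.3 limits the rate to patients followed through the 24 month visit. What can be said is that the patient counts as resolved in the ITT cohort.
- *That the definition favours metal.* The table runs in both directions, and equal points leave the error rate about unchanged. The 21.2% figure needs about 5 of 82 metal patients (0.06 × 82), or 11% of metal failures (6/54), with none in plastic.
- *That any late stent in place at month 24 gives an undefined outcome.* This needs a re-stent at least 12 months after the first stent was lost.

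It is also fair that the proposed failure category adds an investigator-judged indication to an endpoint that has none in its scoring. This is dealt with under the fix.

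**Conclusion.** Both gaps stand on the text. Followed literally, the rule scores effective non-stent treatment of a persistent or recurrent stricture as resolved in the ITT cohort. The Synopsis and Protocol 4.1.2 can class the same re-stent differently when it falls after month 12 with at most 12 cumulative months. The size is unknown: frequency and arm split are not given, every masking figure rests on assumed values, and no direction of bias is shown. One rescored patient matters only at the pass/fail boundary. This should be fixed because it concerns the endpoint that carries the hypothesis test, the trial is non-blinded and the remedy is small. Confidence is medium, since the number of affected patients may be very low.

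**What to change.** Change scoring only, with no change to patient care.

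1. In Protocol 4.1.2 and SAP 7.3, count any non-stent biliary intervention for a persistent or recurrent stricture after the stenting period (surgical, percutaneous, or endoscopic dilation without a stent) as a primary-endpoint failure.
2. Before analysis, reconcile the Synopsis note, Protocol 4.1.2 and 4.1.3, and SAP 7.3 to one scoring definition of the stenting period. It should also state which alkaline phosphatase value is the reference and how a stent in place at month 24 is scored.
3. Report the primary result under the other reading as a sensitivity analysis.

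Cost: endpoint wording in two documents, a check that the CRF captures such interventions and their indication, and one extra table. The indication would be judged by unblinded investigators; a sensitivity analysis counting any such intervention regardless of indication limits this. Resolution rates may be slightly lower.

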4.1.3. Re-stenting

- Re-stenting after the per-protocol 12 month stenting period should only be considered if subjects meet initial criteria for stenting:
 - Symptomatic bile duct stricture (defined by cholangitis or persistent jaundice for at least one month or cholestasis associated with at least 3 times normal alkaline phosphatase level) documented at time of enrollment for naïve stricture or at the time of prior plastic stent placement in strictures that had one prior plastic stent inserted.¹²
 - Common bile duct stricture based on imaging assessment of dilatation of the common and/or intrahepatic bile ducts
- To minimize the risk of recurrent obstructive symptoms due to sludge or stones in the post-stent removal period, every attempt should be made to clear the bile duct of sludge and/or stone (i.e., balloon sweep and/or flushing).

4.2. Secondary Endpoints

1. Occurrence of adverse events related to the stent and/or the stent placement or removal procedures
2. Number of ERCP procedures through 24 months after initial stent placement
3. Ability to deploy the stent(s) in satisfactory position
4. Stent Removal:
 - Ability to remove the stent(s) without serious stent removal related adverse events at each procedure involving removal of stent(s) (technical success at removal) or
 - Complete distal migration without serious stent removal related adverse events
5. Liver Function Tests (LFT's)
 - Baseline LFTs compared to LFTs taken at time of original plastic stent placement for any subject with a prior plastic stent
 - LFT improvement at 1 month post-study treatment compared to baseline LFTs (and/or compared to LFTs taken at time of original plastic stent placement for any subject with a prior plastic stent)
 - LFTs at month 24 compared to LFTs at removal of last stent (applicable for subjects who had not been re-stented at time of month 24 visit)
6. Health Economic Endpoints:
 - Number of outpatient procedures
 - Number of hospitalizations
 - Duration of hospitalizations

- Length of procedures
- Number of devices

5. Design

The study is designed as a post-market, multi-center, prospective, non-blinded, randomized study. At least 164 subjects (82 per arm) will be treated with 1:1 randomization between Group A and Group B and will be followed through 24 months post-initial stent(s) placement:

- Subjects in the MS arm will be treated with a single metal stent, which will be removed 12 months post-placement.
- Subjects in the PS arm will receive 2 plastic stents when possible. Subjects in this arm will undergo plastic stents exchange/bile duct calibration at 4 and 8 month post-initial stent placement. At each stent exchange, the goal should be to provide progressive stent therapy by increasing the number of plastic stents at 4 months and again at 8 months. Final plastic stent removal will occur 12 months post-initial stent placement.

5.1. Inclusion Criteria:

- Age 18 or older
- Willing and able to comply with the study procedures and provide written informed consent to participate in the study
- Chronic pancreatitis
- Symptomatic bile duct stricture (defined by cholangitis or persistent jaundice for at least one month or cholestasis associated with at least 3 times normal alkaline phosphatase levels) documented at time of enrollment for naïve stricture or at the time of prior plastic stent placement in strictures that had one prior plastic stent inserted.¹²
- Common bile duct stricture based on imaging assessment of dilatation of the common and/or intrahepatic bile ducts

5.2. Exclusion Criteria:

- Biliary stricture of benign etiology other than chronic pancreatitis
- Prior biliary metal stent or any plastic stenting other than one plastic stent of 10 Fr or less for 6 months or fewer
- Developing obstructive biliary symptoms associated with an attack of acute pancreatitis
- Biliary stricture of malignant etiology
- Stricture within 2 cm of common bile duct bifurcation
- Known bile duct fistula or leak
- Subjects for whom endoscopic techniques are contraindicated
- Known sensitivity to any components of the stent or delivery system
- Symptomatic duodenal stenosis (with gastric stasis)
- Participation in another investigational study within 90 days prior to consent

- Investigator Discretion

6. Subject Accountability

6.1. *Point of Enrollment*

A subject is considered enrolled after signing the Informed Consent Form (ICF). See Section 8.4 for further information on enrolled, intent-to-treat and per-protocol cohorts.

6.2. *Withdrawal*

All subjects enrolled in the clinical study (including those withdrawn from the clinical study or lost to follow-up) shall be accounted for and documented. If a subject withdraws from the clinical investigation, the reason(s) shall be reported and recorded in the study database. If such withdrawal is due to problems related to investigational device safety or performance, the investigator shall ask for the subject's permission to follow his/her status/condition outside of the clinical study.

While study withdrawal is discouraged, subjects may withdraw from the study at any time, with or without reason, and without prejudice to further treatment. Additional data may no longer be collected after the point at which a subject has been withdrawn from the study or withdraws consent. Withdrawn subjects will not be replaced. All open adverse events should be closed or documented as ongoing. Data collected up to the point of subject withdrawal may still be used.

7. Study Methods

7.1. *Data Collection*

The schedule of observations and assessments to take place during the study follows on the next page.

Table 1. Study Event Schedule

Study Visit	Screening/ Baseline	Treatment	Mo. 1* (30 d)	Mo. 4 (120 d)	Mo. 8 (240 d)	Mo. 11-12 (330-360 d)	Mo 24* (720 d)	Additional ERCP
Window	≤ 5 days prior to treatment	N/A	±10 d	±30 d	±30 d	See range above	±30 d	NA
ICF	X							
Eligibility Assessment	X							
Demographics	X							
Medical History	X							
Liver Function Normal Ranges	X**						X	X****
Liver Function Tests	X		X	***	***	X	X	X
Assessment of Biliary Obstructive Symptoms	X		X			X	X	X****
Randomization		X						
Stent Placement/Exchange		X		PS Only	PS Only			X (if done)
Stent Removal						X		
Cholangiogram or other Common Bile Duct Imaging	X (prior to stent placement)					X (after stent removal)		X (if standard of practice)
AE/Device Malfunction Assessment	Report as occurs/needed per the Protocol Reporting Requirements – See Section 11.							
Protocol Deviations	Report as occurs/needed.							

*Visit may be conducted in the office or via telephone with liver function tests drawn and sent from local clinic/hospital.

**In addition to baseline LFTs, LFTs are also to be collected from time of original plastic stent placement for any subject with a prior plastic stent.

***If subject is not re-stented after Month 4 or 8 Plastic Stent Exchange, Liver Function Tests must be collected at that visit.

****Required for any visit that results in re-stenting

7.2. *Study Candidate Screening*

No study-specific testing will be conducted until after the subject has signed an ICF. A Screen Failure/Enrolled Log will be maintained in EDC by the center to document select information about candidates who signed consent.

7.3. *Informed Consent*

Written Informed Consent must be obtained for all subjects who are potential study candidates. Subjects will be asked to sign the Informed Consent form before any study-specific tests or procedures are performed. The Informed Consent form is study-specific and must be approved by the study Institutional Review Board (IRB)/Ethics Committee (EC). Study personnel should explain that even if a subject agrees to participate in the study and signs the ICF, the ERCP procedure may demonstrate that the subject is not a suitable candidate for the study.

7.4. *Study Visits*

7.4.1. **Screening/Baseline – Visits/Assessments must occur within 5 days prior to stent placement – Office Visit**

- Informed Consent (See Section 7.3)
- Eligibility Criteria Assessment
- Demographics
- Medical History
- Collection of Liver Function Normal Ranges
- Liver Function Tests (at enrollment for naïve strictures or at the time of prior plastic stent placement in strictures that had one prior plastic stent inserted)
 - Alkaline phosphatase – mandatory
 - Total Bilirubin – mandatory
 - Gamma GT – optional
 - SGOT and SGPT (AST, ALT) – optional
- Assessment of Biliary Obstructive Symptoms
 - Right Upper Quadrant Pain
 - Fever/Chills
 - Jaundice
 - Itching
 - Dark urine
 - Pale stools
 - Nausea/Vomiting
- Cholangiogram or other Common Bile Duct Imaging
- Adverse Event/Device Malfunction Assessment

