7.5. Study Completion

Each subject will be followed for 2 years post-initial stent placement. Recurrent strictures will be treated with a metal stent in Group A (MS) and with plastic stents in Group B (PS) – no cross-over. Follow-up will continue until Month 24 after initial stent placement for all subjects, in order to assess all secondary endpoints in a comparative fashion for the MS and PS arms.

Additional visits may be conducted at the Investigator’s discretion in accordance with Adverse Event or Device Malfunction data collection. A subject will be considered lost to follow-up if the subject remains unresponsive to communication after three documented attempts by study staff.

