8.6.2. Post-Procedure Endpoints

Post-procedure information will be collected at regularly scheduled follow-up examinations as detailed in the clinical trial schedule and will be summarized using descriptive statistics for continuous variables and frequency statistics for discrete variables. Estimates of primary and secondary endpoints will be reported by treatment group, as well as differences between treatment groups and their 95% confidence intervals.

Impact of baseline variables on endpoints will be analyzed using logistic regression, ANOVA, stratified methods or Kaplan-Meier methods per section 8.6.1 and the SAP.

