5 ADDITIONAL DATA ANALYSES

5.1 Secondary Endpoints

- 1. Occurrence of adverse events related to the stent and/or the stent placement or removal procedures
- 2. Number of ERCP procedures through 24 months after initial stent placement
- 3. Ability to deploy the stent(s) in satisfactory position
- 4. Stent Removal:

Version AA March 20, 2013 Boston Scientific WallFlex Biliary FC CP RCT SAP 90913894/Ver. AA Page 10 of 13

- a. Ability to remove the stent(s) without serious stent removal related adverse events at each procedure involving removal of stent(s) (technical success at removal) or
- b. Complete distal migration without serious stent removal related adverse events
- 5. Liver Function Tests (LFT's)
 - a. LFT improvement at month 1 compared to baseline naïve stricture or to LFTs at time of plastic stent placement 6 months or fewer prior to enrollment in strictures treated with 1 prior plastic stent.
 - b. LFTs at month 24 compared to removal of last stent (applicable for subjects who had not been re-stented at time of month 24 visit)
- 6. Health Economic Endpoints:
 - Number of outpatient procedures
 - Number of hospitalizations
 - o Duration of hospitalizations
 - Length of procedures

The secondary endpoints will be summarized using descriptive statistics (mean, standard deviation, n, minimum, maximum) for continuous variables and frequency statistics for discrete variables. Statistical testing will be performed using appropriate methods. For analysis of LFT's, McNemar's Test or repeated measures regression model may be used.

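### The month-24 LFT endpoint is limited to subjects not re-stented, so the between-arm difference planned for it would not be a randomised comparison

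*Protocol*

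**What the plan says.** Protocol 4.2 item 5 lists three LFT comparisons. The third sets month-24 LFTs against those at removal of the last stent and is "applicable for subjects who had not been re-stented at time of month 24 visit". SAP 5.1 item 5b carries the same limit: "LFTs at month 24 compared to removal of last stent (applicable for subjects who had not been re-stented at time of month 24 visit".

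Re-stenting is also an outcome. Protocol 4.1.2 names as primary-endpoint failures "subjects who are re-stented during follow-up after the per-protocol stenting period". Protocol 4.1.3 ties re-stenting after the stenting period to the entry criteria: imaging evidence of a stricture together with cholangitis, persistent jaundice or "cholestasis associated with at least 3 times normal alkaline phosphatase level".

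On comparison between arms, Protocol 8.6.2 states: "Estimates of primary and secondary endpoints will be reported by treatment group, as well as differences between treatment groups", with 95% confidence intervals. Protocol 7.5 keeps every subject in follow-up to month 24 "in order to assess all secondary endpoints in a comparative fashion for the MS and PS arms". SAP 5.1 adds unspecified testing of secondary endpoints and says that McNemar's test or a repeated measures model may be used for LFTs.

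No rule covers the subjects excluded from this item. The tipping-point analysis in SAP 3.1.3 concerns missing data for the 24-month resolution rate, not subjects removed by definition.

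**The concern.** The restriction selects subjects on something that happens after randomisation, depends partly on the variable being analysed, and may differ between arms. Subjects whose alkaline phosphatase (ALP) rises enough to lead to re-stenting leave the analysis, and their high values leave with them. The two remaining groups are no longer comparable by design, so a difference with a 95% confidence interval would look like a randomised treatment effect without being one. A reader of the final tables could take similar LFTs in the two arms as evidence of similar biliary drainage, when one arm had simply lost more of its poor results.

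**Working it through.** The documents give no sample size, effect size or variability for this endpoint, so there is no figure of the plan to reproduce. Every ALP value below is an assumption.

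**1. How many subjects could leave.** Inputs: 82 per arm (Protocol 5); literature resolution rates 0.762 metal and 0.611 plastic, and the design rate of 66% (Protocol 8.1 and 8.2).
- Metal: 82 × (1 − 0.762) = 19.5, about 20, leaving about 62.
- Plastic: 82 × (1 − 0.611) = 31.9, about 32, leaving about 50.
- Design rate: 82 × 0.34 = 27.9, about 28 per arm.

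These are upper bounds, because failures on ALP alone are not re-stented and stay in.

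**2. Attenuation when re-stenting follows a rise in ALP.** Let X be the log ratio of month-24 ALP to ALP at last removal, normal with mean m and SD s. Assume 80% of subjects with a ratio above 2 are re-stented and dropped. With c = ln 2, a = (c − m)/s, Q = 1 − Φ(a) and E = mQ + sφ(a), the mean of X among those kept is (m − 0.8E)/(1 − 0.8Q).

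True between-arm ratio 1.25 (m = 0 versus m = ln 1.25 = 0.2231):

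| s | arm | Q | E | re-stented (0.8Q) | mean kept |
|---|---|---|---|---|---|
| 0.6 | better | 0.1240 | 0.1228 | 9.9% | −0.1091 |
| 0.6 | worse | 0.2167 | 0.2245 | 17.3% | 0.0527 |
| 0.8 | better | 0.1931 | 0.2193 | 15.5% | −0.2075 |
| 0.8 | worse | 0.2784 | 0.3307 | 22.3% | −0.0533 |

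Observed ratio: exp(0.0527 + 0.1091) = 1.18 at s = 0.6, and exp(−0.0533 + 0.2075) = 1.17 at s = 0.8. A true ratio of 1.50 becomes 1.33 and 1.32 by the same formula.

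**3. A second model.** Assume a median ALP ratio of 4 in recurrence and 1 otherwise, with recurrence in 24% versus 39%. If a fraction p of recurrences is re-stented, the share of recurrences among those kept is f = R(1 − p)/(1 − Rp) for recurrence rate R, and the geometric mean kept is 4^f. With nobody excluded and nobody re-stented: 4^0.24 = 1.39 versus 4^0.39 = 1.72, a ratio of 1.23.

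| p | f, 24% arm | f, 39% arm | ratio among kept | ratio if drained month-24 values are added back |
|---|---|---|---|---|
| 100% | 0 | 0 | 1.00 | 1.00 |
| 90% | 0.031 | 0.060 | 1.04 | 1.02 |
| 70% | 0.087 | 0.161 | 1.11 | 1.06 |
| 50% | 0.136 | 0.242 | 1.16 | 1.11 |

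The last column is 4^((1 − p) × 0.15), taking re-stented subjects to return to a median ratio of 1. Including their observed month-24 values therefore makes the attenuation slightly worse. By simulation of this model, with log SDs of 0.4 in recurrence and 0.3 otherwise, a composite of re-stenting or ALP above 2 times keeps the contrast: about 25% versus 40% at p = 90%.

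**4. Direction.** Take identical arms with 30% recurrence, but re-stent 90% of recurrences in one and 60% in the other.
- f = 0.03/0.73 = 0.041, so 4^f = 1.06.
- f = 0.12/0.82 = 0.146, so 4^f = 1.22.

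The ratio is 1.16 between arms that do not differ, in favour of the arm that re-stents more.

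**The case against.** The case against rests on four points.

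First, the item is worded as a within-subject change. SAP 7.3 names between-arm tests for removability, adverse events, stricture resolution and number of ERCPs, and LFTs are not on that list. This stands in part: the between-arm contrast comes only from general wording. But Protocol 8.6.2 covers secondary endpoints without exception, and Protocol 7.5 says all of them are to be assessed comparatively.

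Second, the restriction has a purpose: a subject with a stent in place at month 24 has no stent-free value after a last removal. This stands, and it supports the within-arm summary. It does not support a between-arm interval.

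Third, re-stented subjects are already counted as failures in the primary endpoint. This also stands. A reader might infer that the restriction helps the non-inferiority claim; the documents do not support that, because non-inferiority is tested only on resolution and the LFT item has no margin or hypothesis.

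Fourth, a reader might infer that all recurrences are removed, or that the bias always runs towards no difference. Neither follows. Subjects not re-stented whose ALP exceeds 2 times the end-of-stenting level stay in (Protocol 4.1.2). The study is not blinded, so the bias follows the tendency to re-stent as well as recurrence, as step 4 shows. The 80% at a doubling in step 2 is also not the protocol's re-stenting criterion.

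**Conclusion.** The point holds as a defect of one secondary endpoint. Carried out as written, the plan yields a between-arm LFT difference in subsets selected on a post-randomisation outcome, with no safeguard. The contrast would tend to flatter the arm that re-stents more, which is likely but not certainly the arm with more recurrence.

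The size cannot be taken from the documents. Under the assumptions shown, a true ratio of 1.25 appears as about 1.17 to 1.18; in the second model, 1.23 appears as anything from 1.00 to 1.16. In both, the true ratio refers to month-24 values that re-stented subjects would have had without re-stenting, which are never observed. The figures illustrate the mechanism and are not estimates for this trial.

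**What to change.** In SAP 5.1 item 5b:
- Keep the comparison in subjects not re-stented as a within-arm description, with no between-arm test or confidence interval, and report the number re-stented per arm beside it.
- Base any between-arm statement on ALP in all randomised subjects whose month-24 status is known. Either rank subjects re-stented after the per-protocol stenting period worst and use a rank test, or count them as failures in a composite with ALP above a stated threshold.
- Do not substitute the month-24 values of re-stented, drained subjects. Do not mix in LFTs drawn at the re-stenting ERCP: Protocol 7.4.8 collects them, but their timing is set by the event and they are not comparable with month-24 values.
- State whether re-stenting within the 12-month cumulative stenting period removes a subject from the descriptive item, since Protocol 4.1.2 keeps such subjects eligible for the primary endpoint.

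The cost is SAP wording and one derived variable, from data already collected. The downside is that a rank or composite result is less direct than a mean change and overlaps with the primary endpoint, which is why the descriptive table should stay beside it.
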